4.2.3.2 Safety Endpoints

The safety endpoints for this trial have been selected based on previous studies in subjects with grass (adult/pediatric subjects 5 to 65 years of age), ragweed (adult subjects), and/or house-dust mite (adult/pediatric subjects 5 years of age and older) allergies treated with grass (MK-7243), ragweed (MK-3641), or house-dust mite (MK-8237) SLIT tablets, respectively. By assessing the severity and frequency of commonly occurring local AEs, in addition to overall AEs and drug-related AEs, safety and tolerability can be assessed.

In addition, the SLIT Report Card (Section 12.10) will be completed by the subject/parent/guardian, daily for the first ~28 days of dosing, to collect information on local side effects of SLIT that occur within the first 60 minutes after each daily study drug intake. An exploratory review of severity grading will be conducted for identified local AEs as graded programmatically and as assessed by the investigator.

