5.8 Subject Withdrawal/Discontinuation Criteria

Subjects may withdraw consent at any time for any reason or be dropped from the trial at the discretion of the investigator should any untoward effect occur. In addition, a subject may be withdrawn by the investigator or the Sponsor if enrollment into the trial is inappropriate, the trial plan is violated, or for administrative and/or other safety reasons. Specific details regarding discontinuation or withdrawal procedures; including specific details regarding withdrawal from Future Biomedical Research, are provided in Section 7.1.4 – Other Procedures.

Discontinuation from treatment is “permanent”. Once a subject is discontinued, he/she shall not be allowed to restart treatment.

A subject must be discontinued from the trial for any of the following reasons:

- The subject or legal representative (such as a parent or legal guardian) withdraws consent.
- The subject experiences an SAE (not including those only associated with an overdose) which is considered treatment related, OR a causal association cannot be ruled out, OR the cause of the SAE is unknown.
- The subject experiences persistent and escalating adverse reactions in the mouth or throat.
- The subject experiences severe or persistent symptoms of esophagitis.
- The subject experiences an anaphylactic reaction with severe symptoms associated with the investigational treatment.
- The subject experiences a severe asthma exacerbation (such as requiring hospitalization or oral corticosteroid use) or the subject's asthma becomes difficult to control.
- The subject experiences other persistent, intolerable AEs considered to be due to the study treatment, as determined by the investigator or the subject/parent/guardian.

- The subject has a medical condition or personal circumstance which, in the opinion of the investigator and/or Sponsor, places the subject at unnecessary risk through continued participation in the trial or does not allow the subject to adhere to the requirements of the protocol.
- The subject is unable to tolerate the study medication, as perceived by the investigator or subject.
- The subject fails to comply with the dosing (see Sec 7.1.1.15), evaluations, or requirements of the study, despite documentation at the site of repeated efforts to reinforce compliance.
- The subject has a confirmed positive serum pregnancy test.
- The subject becomes pregnant.

5.9 **Subject Replacement Strategy**

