7.2.3.2 Events of Clinical Interest

Selected non-serious and serious adverse events are also known as Events of Clinical Interest (ECI) and must be reported to the Sponsor.

For the time period beginning when the consent form is signed until randomization, any ECI, or follow up to an ECI, that occurs to any subject must be reported within 24 hours to the Sponsor if it causes the subject to be excluded from the trial, or is the result of a protocol-specified intervention, including but not limited to washout or discontinuation of usual therapy, diet, placebo treatment or a procedure.

For the time period beginning at randomization through 14 days following cessation of treatment, any ECI, or follow up to an ECI, whether or not related to the Sponsor's product, must be reported within 24 hours to the Sponsor, either by electronic media or paper. Electronic reporting procedures can be found in the EDC data entry guidelines. Paper reporting procedures can be found in the Investigator Trial File Binder (or equivalent).

Events of clinical interest for this trial include:

1. an overdose of Sponsor's product, as defined in Section 7.2.1 - Definition of an Overdose for This Protocol and Reporting of Overdose to the Sponsor, that is not associated with clinical symptoms or abnormal laboratory results.
2. an elevated AST or ALT lab value that is greater than or equal to 3X the upper limit of normal and an elevated total bilirubin lab value that is greater than or equal to 2X the upper limit of normal and, at the same time, an alkaline phosphatase lab value that is less than 2X the upper limit of normal, as determined by way of protocol-specified laboratory testing or unscheduled laboratory testing.*

*Note: These criteria are based upon available regulatory guidance documents. The purpose of the criteria is to specify a threshold of abnormal hepatic tests that may require an additional evaluation for an underlying etiology. The trial site guidance for assessment and follow up of these criteria can be found in the Investigator Trial File Binder (or equivalent).

3. Anaphylactic reactions, anaphylaxis and/or systemic allergic reactions.
4. Events treated with epinephrine.
5. Severe local swelling or edema of the mouth and/or throat.
6. Severe drug-related asthma exacerbations.
7. Eosinophilic esophagitis.

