8.2.5.2 Statistical Methods for Safety Analyses

Safety and tolerability will be assessed by clinical review of all relevant parameters including adverse experiences (AEs), laboratory tests, and vital sign measurements.

The analysis of safety results will follow a tiered approach (Table 11). The tiers differ with respect to the analyses that will be performed. Tier 1 safety endpoints will be subject to inferential testing for statistical significance with p-values and 95% CIs provided for between-group comparisons. Tier 2 safety endpoints will be evaluated via point estimates and 95% CIs for between-group comparisons. Tier 3 safety endpoints will be evaluated via point estimates only.

For this trial, Tier 1 safety endpoints include:

- Proportion of subjects reporting pre-specified local application site reactions (including adverse events related to lip swelling/edema, mouth swelling/edema, palatal swelling/edema, swollen tongue/edema, oropharyngeal swelling/edema, pharyngeal edema/throat tightness, oral pruritus, throat irritation, tongue pruritus, and ear pruritus);
- Proportion of subjects reporting anaphylaxis and/or systemic allergic reactions;

- Proportion of subjects treated with epinephrine.

For the analysis of “Proportion of subjects treated with epinephrine”, the denominator will include all subjects in the ASaT population, regardless of whether self-injectable epinephrine was provided or not. Meanwhile, a sensitivity analysis will be conducted where the denominator will include subjects in the ASaT population who were provided with self-injectable epinephrine, and the numerator will be subjects from the denominator subjects who were treated with epinephrine.

Tier 2 safety endpoints for this trial include:

- Proportion of subjects with any AE;
- Proportion of subjects with any serious AE;
- Proportion of subjects with any drug-related AE;
- Proportion of subjects with any serious and drug-related AE;
- Proportion of subjects who discontinue due to an AE;
- Proportion of subjects with specific AEs or SOCs (incidence \geq 1% subjects in one or more of the treatment groups).

The Tier 1 and Tier 2 safety endpoints will be analyzed using the stratified Miettinen and Nurminen method [1985] with baseline asthma status and age group as stratification factors.

Tier 3 safety endpoints for this trial include:

- Change from baseline in laboratory test parameters at each post-baseline visit;

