### 3.2.5.2 Statistical Methods for Safety Analyses

Safety and tolerability will be assessed by clinical review of all relevant parameters including adverse experiences (AEs), laboratory tests, and vital sign measurements.

The analysis of safety results will follow a tiered approach [Table 4]. The tiers differ with respect to the analyses that will be performed. Tier 1 safety endpoints will be subject to inferential testing for statistical significance with p-values and 95% CIs provided for between- group comparisons. Tier 2 safety endpoints will be evaluated via point estimates and 95% CIs for between-group comparisons. Tier 3 safety endpoints will be evaluated via point estimates only.

For this trial, Tier 1 safety endpoints include:

- Proportion of subjects reporting pre-specified local application site reactions (including adverse events related to lip swelling/edema, mouth swelling/edema, palatal swelling/edema, swollen tongue/edema, oropharyngeal swelling/edema, pharyngeal edema/throat tightness, oral pruritus, throat irritation, tongue pruritus, and ear pruritus);
- Proportion of subjects reporting anaphylaxis and/or systemic allergic reactions;
- Proportion of subjects treated with epinephrine.

For the analysis of “Proportion of subjects treated with epinephrine”, the denominator will include all subjects in the ASaT population, regardless of whether self-injectable epinephrine was provided or not. Meanwhile, a sensitivity analysis will be conducted where the denominator will include subjects in the ASaT population who were provided with self-injectable epinephrine, and the numerator will be subjects from the denominator subjects who were treated with epinephrine.

Tier 2 safety endpoints for this trial include:

- Proportion of subjects with any AE;
- Proportion of subjects with any serious AE;
- Proportion of subjects with any drug-related AE;
- Proportion of subjects with any serious and drug-related AE;
- Proportion of subjects who discontinue due to an AE;
- Proportion of subjects with specific AEs or SOCs (incidence  $\geq$  1% subjects in one or more of the treatment groups).

The Tier 1 and Tier 2 safety endpoints will be analyzed using the stratified Miettinen and Nurminen method [1985] with baseline asthma status and age group as stratification

factors.

Tier 3 safety endpoints for this trial include:

- Change from baseline in laboratory test parameters at each post-baseline visit;

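### Three events of clinical interest (severe mouth/throat swelling, severe drug-related asthma exacerbation, eosinophilic esophagitis) have no pre-specified between-arm estimate with a confidence interval at their own definition

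*SAP*

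**What the plan says.** Protocol 7.2.3.2 lists seven events of clinical interest. After randomization each one "must be reported within 24 hours to the Sponsor, either by electronic media or paper". The list includes "Severe local swelling or edema of the mouth and/or throat", "Severe drug-related asthma exacerbations" and "Eosinophilic esophagitis". Two other entries, anaphylaxis or systemic allergic reactions and events treated with epinephrine, have matching Tier 1 endpoints.

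The tiers are set out in Protocol 8.2.5.2 (Table 11) and sSAP 3.2.5.2 (Table 4):

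- **Tier 1** (p-value and 95% CI, no incidence cut) includes a composite of local application site reactions. It covers swelling of the lip, mouth, palate, tongue, oropharynx and pharynx, together with oral, tongue and ear pruritus and throat irritation.
- **Tier 2** (95% CI, no p-value) has all-cause rows for any, serious, drug-related, serious drug-related and discontinuing AEs. It also has "Proportion of subjects with specific AEs or SOCs", restricted to those reaching 1% of subjects in at least one arm.
- **Tier 3** holds SOC summaries for the same AE categories and AE summaries by asthma status. The rule is "Tier 3 safety endpoints will be evaluated via point estimates only".

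Tier 1 and Tier 2 use the Miettinen-Nurminen method stratified by baseline asthma status and age group. Maximum intensity is an element evaluated for every AE (Protocol Table 7), but no tier uses it. The only planned use of intensity is the exploratory comparison of two grading methods for local events on the SLIT Report Card.

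**The concern.** The sponsor marked these three events out for rapid reporting, so a reader would expect each to have its own by-arm result. None does, and the reason differs by event.

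- **Severe mouth/throat swelling.** The gap is the missing severity split. Tier 1 has no cut, so swelling is always counted, but a severe case counts the same as mild itching. Footnote b of the safety tables keeps the Tier 2 specific-term row for endpoints not already pre-specified, so swelling terms may not get separate rows there either.
- **Eosinophilic esophagitis.** The gap is the 1% cut.
- **Severe drug-related asthma exacerbation.** Both gaps apply. Below 1% the term gets no CI. Above 1% an asthma term is counted at any intensity.

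The stake is interpretive. This is the first trial of the product in subjects under 18. The current amendment was made mainly to add a discontinuation criterion to Protocol 5.8 after the Reference Safety Information was updated: "The subject experiences a severe asthma exacerbation (such as requiring hospitalization or oral corticosteroid use". If a few such cases fall mostly in one arm, the plan commits to no specific estimate or bound, and a row chosen after unblinding would carry less weight.

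**Working it through.** **1. Inputs.** About 1000 subjects randomized 1:1 (sSAP 3.2.8) give about 500 per arm. The safety population is everyone who took a dose (sSAP 3.2.4.2), so later dropouts stay in. The documents state no rate for any of the three events and no share of subjects with asthma. The rates below are assumptions shown over a range.

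**2. What the 1% cut means in subjects.** 0.01 × 500 = 5. At the plan's evaluable number, 1000 × 0.85 / 2 = 425 and 0.01 × 425 = 4.25, so the smallest qualifying count is again 5. A term seen in 1 to 4 subjects in each arm gets no Tier 2 interval.

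**3. Chance that an arm stays below the cut.** P(X ≤ 4) for X ~ Binomial(500, p):

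| Assumed true risk p | P(4 or fewer of 500) |
|---|---|
| 0.25% | 99% |
| 0.5% | 89% |
| 0.75% | 68% |
| 1.0% | 44% |

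At p = 0.5% the chance of at least one case in the arm is 1 − 0.995^500 = 92%, so cases would probably occur and probably get no interval. If both arms had 0.5%, the chance that either reaches 5 is 1 − 0.892² ≈ 20%.

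**4. What the planned method would report.** The Miettinen-Nurminen limits are the values of δ that solve (p1 − p2 − δ)² / V(δ) = 1.96². Here V(δ) = [r1(1 − r1)/n1 + r2(1 − r2)/n2] × N/(N − 1), where r1 and r2 are the maximum-likelihood risks under r1 − r2 = δ. This is the unstratified form; the plan stratifies. With 500 per arm, in percentage points:

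| Active vs placebo | Difference | 95% CI |
|---|---|---|
| 0 vs 0 | 0.0 | −0.76 to 0.76 |
| 1 vs 0 | 0.2 | −0.56 to 1.12 |
| 2 vs 0 | 0.4 | −0.36 to 1.45 |
| 3 vs 0 | 0.6 | −0.17 to 1.75 |
| 4 vs 0 | 0.8 | 0.03 to 2.04 |
| 4 vs 1 | 0.6 | −0.40 to 1.86 |

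Of these splits only 4 vs 0 excludes zero, and narrowly.

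**5. Concentration in subjects with asthma.** If exacerbations occur only in that stratum, the largest stratum risk that still falls below the cut is 4 / (500 × share). That is 4/150 = 2.7%, 4/200 = 2.0% and 4/250 = 1.6% at assumed shares of 30%, 40% and 50%. For 4/200 vs 0/200 the interval is 0.09 to 5.03 points.

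Steps 2 to 5 concern the cut. They apply to asthma exacerbation and, except for step 5, to eosinophilic esophagitis. They do not apply to swelling.

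**The case against.** The strongest reply is that these events are not left out of the analysis, and that is correct. A reader might infer that they sit in no tier, or that the trial would yield no between-arm information on them. The documents do not support either. Swelling is in an uncut Tier 1 endpoint. Serious, drug-related and discontinuing cases enter uncut Tier 2 rows with intervals. Tier 3 gives SOC summaries separately for serious, drug-related and discontinuing AEs, and AE summaries by asthma status. Because a severe exacerbation requires discontinuation under Protocol 5.8, it should appear in the discontinuation summaries, although only by class or within an all-cause total. Lung function, asthma symptom score, SABA use and nocturnal awakenings are also compared, and an external committee reviews safety.

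A reader might also take Protocol 4.2.3.2 as a general promise to analyse severity. It says "By assessing the severity and frequency of commonly occurring local AEs, in addition to overall AEs and drug-related AEs, safety and tolerability can be assessed". The severity commitment covers common local events only, and graded intensity for local events is planned, if only as exploratory work. It does not extend to asthma or eosinophilic esophagitis.

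A third tempting reading is that the cut would hide a clear imbalance. Step 4 does not bear that out: 3 vs 0 and 4 vs 1 include zero, and 4 vs 0 excludes it by 0.03 points without stratification.

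What survives is narrower. None of the planned outputs gives an estimate with an interval for any of the three events as Protocol 7.2.3.2 defines it. The exploratory grading cannot fill the gap. It covers report-card local events in about the first 28 days, within 60 minutes of dosing. Its programmatic severe grade means symptomatic medication plus discontinuation, which is not the Table 7 scale. No between-arm estimate is specified for it.

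**Conclusion.** The point holds as a gap in pre-specified reporting. Three events singled out for 24-hour reporting have no between-arm estimate with a CI at their own definition: severe swelling for want of a severity split, eosinophilic esophagitis because of the 1% cut, and severe drug-related asthma exacerbation because of both. For the two events subject to the cut, an arm of 500 would stay below it with probability 89% at an assumed risk of 0.5% (99% at 0.25%, 44% at 1%).

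This should be corrected, but its reach is limited. No primary or key secondary conclusion depends on it. What is gained is a stated estimate and an upper bound on risk: even 0 vs 0 would bound the difference at 0.76 points. The result rests on assumed rates and an assumed asthma share, and on unstratified intervals that may move slightly under the planned stratification.

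**What to change.** In sSAP 3.2.5.2 / Table 4, and to match in Protocol 8.2.5.2 / Table 11, add these Tier 2 rows, exempt from the 1% cut, with the same stratified Miettinen-Nurminen 95% CI:

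- (a) subjects with an AE of asthma exacerbation of severe maximum intensity, shown regardless of causality and also restricted to drug-related (the Protocol 7.2.3.2 definition), overall and by baseline asthma status;
- (b) subjects with severe swelling or edema of the mouth and/or throat;
- (c) subjects with eosinophilic esophagitis;
- (d) subjects with any severe AE, plus a descriptive by-arm table of AEs by maximum intensity.

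List the AE terms that count for (a) to (c) before unblinding. Do not use the whole asthma criterion of Protocol 5.8 as the case definition for (a), because it also covers asthma that becomes difficult to control and would label other cases as severe exacerbations.

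The cost is analysis text, a few rows and one table, using the planned method and the intensity and causality that Protocol Table 7 already calls for. Both documents allow non-confirmatory changes through the sSAP before database lock. The downside is a few more wide intervals without multiplicity control; Tier 2 carries no p-values, so the efficacy testing sequence is unaffected. Clinical management and reporting rules stay as they are.

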AE = adverse event; CI = confidence interval; SOC = System Organ Class; X = results will be provided. a Adverse Experience references refer to both Clinical and Laboratory AEs. b Includes only those endpoints not pre-specified as Tier 1 or Tier 2 endpoints.				

In addition, the SLIT Report Card (Section 4.2.3.2 of the protocol) will be completed by the subject/parent/guardian, daily for the first ~28 days of dosing, to collect information on local side effects of SLIT that occur within the first 60 minutes after each daily study drug intake. Adverse events identified by the WAO as local side effects of SLIT include the following: dysgeusia, oral pruritus, swelling of lips, mucosal edema, ear pruritus, swollen tongue, glossodynia, mouth ulceration, tongue ulceration, throat irritation, pharyngeal edema, nausea, abdominal pain upper/abdominal pain, vomiting, and diarrhea.

Identified local AEs will be graded via a programmatic approach and clinical review as mild, moderate, or severe. An exploratory review of the intensity grading via 2 different methods, the programmatic approach using the WAO grading system and grading as determined by the investigator’s review of the AEs with their subjects/parents/guardians, will be conducted.

The WAO grading system for SLIT local adverse events defines intensity as follows:

Mild (Grade 1)	Not troublesome and no symptomatic treatment required and no discontinuation of SLIT because of local side effects
Moderate (Grade 2)	Troublesome or requires symptomatic treatment and no discontinuation of SLIT because of local side effects
Severe (Grade 3)	Grade 2 and SLIT discontinued because of local side effects

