The WAO local AE intensity grading was modified in that subjects collect the information on the presence of the AEs on the SLIT Report Card but do not indicate if they consider the AE “troublesome” or “not troublesome.” Subjects also indicate if a medication is utilized to treat the AE and information regarding discontinuation due to the AE is also collected. The WAO intensity grading for local AEs will be determined programmatically. Essentially, mild intensity (Grade 1) will be assigned to events that do not result in symptomatic use of a medication. If an AE results in use of a symptomatic medication to treat the AE, it is assigned an intensity of moderate (Grade 2) and considered troublesome; if an AE results in the use of a symptomatic medication and in discontinuation from treatment, it is assigned an intensity of severe (Grade 3).

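### The programmatic WAO grading calls a local reaction mild when it ended treatment without symptomatic medication, although the printed WAO table rules out discontinuation for Grade 1

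*SAP*

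**What the plan says.** Supplemental SAP section 3.2.5.2 first prints the WAO scale for local reactions to sublingual immunotherapy:

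- Grade 1: "Not troublesome and no symptomatic treatment required and no discontinuation of SLIT because of local side effects".
- Grade 2: "Troublesome or requires symptomatic treatment and no discontinuation of SLIT because of local side effects".
- Grade 3: "Grade 2 and SLIT discontinued because of local side effects".

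It then explains that the scale was modified because the Report Card does not ask whether an event was troublesome. Medication use is recorded on the card, and "information regarding discontinuation due to the AE is also collected".

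The rule to be programmed follows. For Grade 1: "Essentially, mild intensity (Grade 1) will be assigned to events that do not result in symptomatic use of a medication". An event treated with symptomatic medication is Grade 2 and counts as troublesome. For Grade 3: "if an AE results in the use of a symptomatic medication and in discontinuation from treatment, it is assigned an intensity of severe".

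The purpose is given as "An exploratory review of the intensity grading via 2 different methods", the other method being the investigator's own grading.

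**The concern.** The programmed rule looks at discontinuation only after medication has been used. An event that made the child stop treatment, but for which nothing was taken, goes to the lowest grade. The printed scale does not allow that: Grades 1 and 2 both require that treatment was not stopped because of local side effects, and only Grade 3 admits stopping.

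The combination can occur. Protocol section 5.8 lists among the reasons for mandatory discontinuation: "The subject experiences persistent and escalating adverse reactions in the mouth or throat". It attaches no condition that medication was used.

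What is at stake is the comparison of the two grading methods. If treatment-ending events are coded mild by construction, part of any disagreement with the investigators comes from the coding and not from the events. A table presented as WAO grading would also contradict the definition printed above it.

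**Working it through.** No sample size, power or error rate is involved, so the check is an enumeration.

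**Inputs**, all from supplemental SAP section 3.2.5.2: the three printed WAO definitions, the programmed rule, and the statement of which items are collected.

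**Notation.** T = troublesome (not collected), M = symptomatic medication (collected), D = discontinued because of the event (collected); 1 = yes, 0 = no.

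**Printed scale.** Grade 1 if T = 0, M = 0 and D = 0. Grade 2 if (T = 1 or M = 1) and D = 0. Grade 3 if (T = 1 or M = 1) and D = 1. For Grade 3 an assumption is needed. Its definition contains Grade 2, which itself requires no discontinuation, so I read the reference as the first clause of Grade 2 only (troublesome or treated).

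**Programmed rule.** Grade 1 if M = 0. Grade 2 if M = 1 and D = 0. Grade 3 if M = 1 and D = 1.

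**Proposed rule.** Grade 3 if D = 1. Otherwise Grade 2 if M = 1, and Grade 1 if M = 0.

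| T | M | D | Printed WAO | Programmed | Proposed |
|---|---|---|---|---|---|
| 0 | 0 | 0 | 1 | 1 | 1 |
| 0 | 0 | 1 | none | 1 | 3 |
| 0 | 1 | 0 | 2 | 2 | 2 |
| 0 | 1 | 1 | 3 | 3 | 3 |
| 1 | 0 | 0 | 2 | 1 | 1 |
| 1 | 0 | 1 | 3 | 1 | 3 |
| 1 | 1 | 0 | 2 | 2 | 2 |
| 1 | 1 | 1 | 3 | 3 | 3 |

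**Result.** The programmed rule departs from the printed scale in 3 of 8 rows.

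- Troublesome, untreated, not discontinued (WAO 2, programmed 1). This follows from the missing T item and is covered by the declared modification.
- Troublesome, untreated, discontinued (WAO 3, programmed 1).
- Not troublesome, untreated, discontinued (no printed grade, programmed 1).

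The last two rows form a single cell in the collected data, M = 0 and D = 1. Whatever T was, the printed scale never gives Grade 1 there, and the program always does. Under the proposed rule the second mismatch disappears, the third is settled by a stated convention, and only the declared one remains.

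**Illustration of size.** Let s be the share of discontinuations for Report Card local reactions in which no medication was taken. The programmed scale records 1 − s of them as Grade 3:

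- s = 0: 100%
- s = 0.25: 75%
- s = 0.5: 50%
- s = 1: 0%

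The documents give neither s nor the number of such discontinuations, so these are assumed values and no event count follows.

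**The case against.** The strongest reply is that medication stands in for the missing troublesome rating. Put that proxy into the printed Grade 3 and the result is exactly the programmed Grade 3, medication plus discontinuation. On this view an untreated event fails to reach Grade 3 because of the declared modification. That part stands: it explains the Grade 3 wording. It does not explain Grade 1, where absence of discontinuation is a separate condition that needs no rating of troublesomeness. That condition was dropped without being mentioned.

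Second, the printed scale does not fully settle the cell. Grade 3 is circular if read literally, and an untreated event that was not troublesome but ended treatment has no grade. This also stands, so assigning Grade 3 there is a convention and must be labelled as one. It is the natural convention, since Grade 3 is the only printed grade that admits discontinuation.

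Third, the word that opens the programmed rule marks it as a summary. Neither document contains a fuller algorithm, so a programmer following the text would output Grade 1.

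Fourth, the reach is narrow and the 1 − s figures are an identity, not evidence. Both are true. Protocol section 5.8 shows that discontinuation does not depend on medication; it does not show that such an event will fall within the Report Card window (60 minutes after intake, first 28 days or so). The count may be zero.

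**Conclusion.** The concern holds. As written, the rule gives an untreated local reaction that ended treatment a grade that the printed scale excludes, and the item needed to avoid this is already collected. Because Grade 1 is the lowest grade, any error in this cell runs downward. That Grade 1 is excluded does not depend on how the circular Grade 3 definition is read; that Grade 3 is the right replacement does, together with the convention that stopping treatment shows the event was troublesome.

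The consequence is confined to the exploratory comparison of programmatic and investigator grading. The Tier 1 proportion with local application site reactions, the Tier 2 proportion discontinuing due to an adverse event, the system organ class summaries of events leading to discontinuation and the investigator's severity rating are unaffected. The plan should be corrected, but no confirmatory conclusion depends on it.

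**What to change.** In supplemental SAP section 3.2.5.2, apply discontinuation first:

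- Grade 3: a local reaction that led to discontinuation of study drug, with or without medication.
- Grade 2: symptomatic medication without discontinuation.
- Grade 1: neither.

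Add to the declared modification that discontinuation because of the event is taken as evidence that it was troublesome. Report by arm the number of events with discontinuation and no medication, so that the effect of the convention is visible.

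The cost is one sentence, one line of programming and one table row, with no new data. Protocol section 8.2 and supplemental SAP section 3.2 both place changes to exploratory analyses, made before database lock, in the supplemental SAP, so no protocol amendment is needed.
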